malnutrition is assessed in children and adults, the feet and lower legs must be examined for edema to rule out edematous malnutrition which invalidates those anthropometric indices which include weight. Such examination will be done by qualified medical personnel and be as noninvasive as possible. In many children, some measure of mild restraint is required for certain portions of such examinations. Such restraint is minimized and carried out only with parents' permission or by parents themselves.

Collection of biologic specimens. For most micronutrients, clinical manifestations appear late in the deficiency and only among those persons with severe deficiency. As a result, clinical findings almost always underestimate the prevalence of the micronutrient deficiency. For this reason, many nutrition assessment surveys include the collection of biologic specimens in order to obtain more accurate estimates of the prevalence rates and severity of deficiencies of specific micronutrients. The most common micronutrient deficiencies assessed include iron and vitamin A; however, others may be included in specific surveys. The type of specimens, the methods of obtaining the specimen, and target groups for the laboratory assessment of specific micronutrient deficiencies in emergency-affected populations are shown below.

Micronutrient	Specimen	Methods of collection	Common target groups
Iron	Blood	Fingerstick or	Children < 5 years of age
IIOII	Diood	Phlebotomy	Adult women
		Fingerstick or	Children < 5 years of age
Vitamin A	Blood	Phlabotomy	Adult women
		rinebotoniy	Adolescents
P vitamina	Plood	Phlahotomy	Children < 5 years of age
D vitaliilis	Blood	rmebotomy	Adolescents
Vitamin D	Blood	Phlebotomy	Children < 5 years of age
Vitamin C	Blood	Phlebotomy	All ages and sexes
Iodine	Urine	Voluntary urination	Children 8-11 years of age

Information management and analysis software

In most cases, initial data entry and analysis for nutrition assessment surveys in emergency-affected populations will be done using EpiInfo software. In cases where the final report must await the results of laboratory results, the final data analysis can be done using SAS or SUDAAN.

Data entry, editing and management, including handling of data collection forms, different versions of data, and data storage and disposition

For most nutrition assessment surveys in emergency-affected populations, computer data entry will be done one time, followed by a complete comparison of the paper data collection forms and computer data to ensure accuracy. After this comparison and further data cleaning, all preliminary copies of the dataset will be erased and the final dataset distributed to concerned parties. The computer database variable names will be added to a copy of the data collection form to indicate precisely the origin of the data in each field of the database. This reference document will be stored both electronically with the computer dataset and in hardcopy along with the paper data collection forms. The final dataset and all other materials created or used during the survey will belong to the organization or agency which has requested IERHB assistance and paid the costs of the survey, including the expenses of IERHB personnel. However, because many of these organizations have little technical capacity in data storage, analysis, or interpretation, IERHB personnel will maintain a copy of the final dataset in order to be able to answer queries and perform additional analyses not included in the written survey report. Authorship of publications based on the results of a nutrition assessment survey will be discussed by all concerned parties and agree upon before preparation of any publications. Such publications must be reviewed and approved by each of the organizations which participated in the survey.

The actual paper data collection forms will not contain identifying information. As a result, the computer dataset will also not contain any identifying information. However, in most surveys, a sample list is created when the final selection of households or individuals is made during the sampling process. In cluster surveys, there is a separate form for each cluster, often called a cluster control form, which lists all the households or individuals selected for that cluster. These sample lists and cluster control forms contain both identifying information and a numeric code for each selected household or individual. This code allows survey workers to match the identifying information on the sample list to individual data collection forms, thus permitting follow-up with specific survey participants if necessary. At the end of the survey, these sample lists will be destroyed or permanently and securely stored in a location separate from the data collection forms. Final deposition of survey materials, including computer datasets and paper forms, will be determined by the organization or agency which funds the survey. In most cases, the sample lists and paper data collection will not return to Atlanta with IERHB personnel.

Quality control/assurance

During data collection at each selected household, survey team leaders will supervise all steps of data collection, including the interview, physical examination, anthropometric measurement, and biologic specimen collection. Upon completion of data collection at each household, the survey team leader will review the entire data collection form to ensure completeness and accuracy. As mentioned above, after data entry, the computer dataset will be exhaustively compared to the original paper data collection forms to ensure accurate data entry.

Bias in data collection, measurement and analysis

Several source of bias may potential influence the results of a nutrition assessment survey in an emergency-affected population.

Interview. Survey interviewers may influence the answers given by survey participants. To reduce this bias, interview questions will be carefully written and pretested on individuals from the target population. Translation and backtranslation will ensure that questions collect the data they are meant to collect. Survey interviewers will be carefully trained and supervised to ensure that they read questions verbatim from the data collection form. Most questions will be relatively simple and not require extensive interpretation by respondents.

Anthropometric measurements. As mentioned above, complete training is provided in measurement technique and includes a standardization exercise. Survey trainees who cannot achieve measurement results comparable to those of other survey workers and supervisors will

not be used for actual data collection. The height boards, scales, and tapes used for measurement will be carefully constructed and calibrated periodically throughout the data collection period. During data analysis, outlying anthropometric indices will be excluded from analysis according to the criteria recommended by the WHO. Additional analysis will be done to judge the validity of anthropometric measurements, including an analysis for digit preference in height measurements, calculation of the standard deviations of all z-scores, and analysis of the age distribution of selected children 6-59 months of age by one-month intervals.

Physical examination. Training for survey workers who examine survey participants will use photographs of the signs of various micronutrient deficiencies. Team supervisors will confirm all positive findings during data collection.

Biologic specimen collection. Training for survey workers covers all aspects of specimen collection and any laboratory testing to be done in the field. For example, for surveys measuring hemoglobin concentration, training includes all the aspects of obtaining fingerstick blood and operating and calibrating the Hemocue® hemoglobinometer. Biologic specimens are processed, stored, and transported according to instructions from the laboratory which does the testing.

Intermediate reviews and analyses

Because most nutrition assessment surveys in emergency-affected populations are done relatively rapidly, no intermediate tracking of results can be done before the final data analysis. Nonetheless, continuous supervision provides quality control during data collection.

Limitations of study

Surveys to assess nutritional status in emergency-affected populations are subject to the same limitations as all cross-sectional surveys. Nonetheless, the components of training and supervision outlines above will minimize these threats to validity (see section above "Bias in data collection, measurement and analysis").

Handling of Unexpected or Adverse Events

Identifying, managing, and reporting adverse events

The only adverse events possible in nutritional assessment surveys in emergency-affected populations are those which may appear, albeit very rarely, after fingerstick or phlebotomy. Only qualified survey team members are allowed to perform these procedures, and these personnel monitor survey participants for some minutes after the procedure to ensure that there is no bleeding, serious bruising, or vasovagal syncope.

Emergency care

Vasovagal syncope is the only event which might be construed by a layperson as an emergency resulting from data collection activities. Survey team members are trained to place a survey participant with vasovagal syncope in a recumbent position and explain to the participant and family members the nature of the syncope and its immediately reversible and nondangerous nature.

Notifying participants of their individual results

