In populations with such extensive food shortages and severe malnutrition, relief organizations must supply emergency food in order to prevent widespread mortality. In order to initiate such life-saving interventions, relief workers must carry out assessments to determine the specific needs in each population. However, the relief food provided to emergency-affected populations is often deficient in many important micronutrients, such as iron, vitamin A, B vitamins, and others. As a result, although a relief operation may provide sufficient protein, energy, and fats, many individuals in the recipient population may manifest symptoms and signs of micronutrient deficiencies.

Both the initial assessment of an emergency-affected population and evaluation of existing food and nutrition programs require reliable data about the prevalence and severity of proteinenergy and micronutrient malnutrition. Such data are usually gathered by population-based surveys. This protocol describes the activities which are commonly included in such assessment surveys.

Intended and potential use of the findings

As stated above, organizations providing aid to emergency-affected populations need data on the type, prevalence, and severity of nutritional deficiencies in order to plan nutritional interventions. For example, the type of feeding programs implemented in a relief dependent population is often largely determined by the prevalence of acute protein-energy malnutrition in children less than 5 years of age. If acute protein-energy malnutrition is not very common, there may be no need for programs providing nutritional rehabilitation for individual children. If malnutrition is widespread, several different types of nutritional rehabilitation, including supplemental and therapeutic feeding, should be offered. In addition, specific programs, such as iron supplementation of pregnant women or children less than 5 years of age, should not be implemented without some indication that iron deficiency is a substantial public health problem in a specific population.

After the acute emergency period, when death rates have normalized and adequate health and public health programs are in place, nutrition assessment surveys are a valuable tool for outcome evaluation of various nutrition programs.

Study design and locations

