Nutrition assessment surveys are most commonly cross-sectional descriptive surveys used to estimate the prevalence rates of various types of malnutrition. Surveys can also assess the role of risk factors and identify vulnerable subgroups. Surveys will often be carried out in many different situations and populations, such as 1) in refugee camps or camps for internally-displaced persons which are organized and run by local government authorities or international organizations; 2) in displaced populations which are integrated into a local host population; and 3) in emergency-affected populations which are not displaced. Surveys in non-displaced populations are similar to those done in stable populations not affected by emergencies.

Objectives

The objectives of nutrition assessment surveys in emergency-affected populations usually include at least some of the following:

- 1) Estimate the current prevalence of acute malnutrition (wasting) and chronic malnutrition (stunting) among children 6-59 months of age.
- 2) Estimate the current prevalence of protein-energy malnutrition among women of childbearing age (15-49 years of age).
- 3) Estimate the current prevalence and severity of anemia among children 6-59 months of age, women of child-bearing age, and possibly adult men age.
- 4) Estimate the current prevalence and severity of vitamin A deficiency among children 6-59 months of age and women of child-bearing age.
- 5) Estimate the current prevalence and severity of other micronutrient deficiencies in various target population groups. Such deficiencies and target groups may include iodine deficiency in children 8-11 years of age; B vitamin deficiency in children, adolescents, or adults; vitamin D deficiency in children 6-59 months of age; or others.
- 6) Estimate current household food consumption patterns, household food security, and food consumption in children 6-59 months of age.
- 7) Estimate the measles immunization coverage among children 9-59 months of age.
- 8) Estimate the cumulative 2-week prevalence of diarrheal disease and acute lower respiratory infection in children 6-59 months of age.
- 9) Estimate the crude mortality rate and age-specific mortality rate for children less than 5 years of age.

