Nutrition assessment surveys described herein will be carried out most often among displaced or emergency-affected populations. Such populations, if displaced, are sometimes settled in camps and sometimes integrated into the host community or both. Regardless of pattern of settlement, surveys will often select a sample of households and include in the survey sample all members of targeted groups who reside in those households on the day of data collection. Targeted groups may include children less than 5 years of age, women of childbearing age, school age children, adolescents, adult men, or other groups depending on the nutritional conditions to be assessed.

Case definitions

Case definitions for nutritional deficiencies commonly included in nutritional assessment surveys in emergency-affected populations are given below:

Protein-energy malnutrition in children less than 5 years of age: Undernutrition, including wasting, stunting, and underweight, in children less than 5 years of age is defined using the NCHS:CDC:WHO reference population of children. When it becomes available, the new World Health Organization (WHO) international reference population will be used instead. Children with z-scores below -2 for weight-for-height, height-for-age, or weight-for-age are defined as wasted, stunted, or underweight, respectively. Moderate wasting, stunting, and underweight are defined as a z-score less than -2 but greater than -3. Z-scores less than -3 define severe wasting, severe stunting, or severe underweight.

For children less than 5 years of age, mid-upper arm circumference (MUAC) is sometimes used to assess protein-energy malnutrition when measuring weight and height are not feasible. MUAC measurements less than 11.5 cm are classified as severely low. MUAC measurements of 11.5 - 12.4 cm are considered moderately low, and MUAC 12.5 cm or greater are considered normal.

Protein-energy malnutrition in adults: Malnutrition in adults is assessed using body mass index (BMI), which is calculated by dividing the weight in kilograms by the square of the standing height in meters. The most common cut-off points for BMI to define levels of malnutrition in nonpregnant adults are shown below.

BMI	Category of malnutrition
< 16.0	Severe
16.0 - 16.9	Moderate
17.0 - 18.4	At risk
18.5 - 24.9	Normal
25.0 - 29.9	Overweight
> 30	Obese

An alternate scheme uses both MUAC and BMI to determine the level of malnutrition according to the scheme shown below.

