	Per son no.	Age (years)	Sex (circle one)	Curren as of T (circl	nt Status TODAY le one)	If missing or dead, since when? (mm/yy)	Died of which cause? (ask questions)	Walnutrition?	Pregnant or in Chel??
\vdash	1		M / F	1 2	3 4	/		Y / N	Y / N
	2		M / F	1 2	3 4	/		Y / N	Y / N
	3		M / F	1 2	3 4	/		Y / N	Y / N
	4		M / F	1 2	3 4	/		Y / N	Y / N
	5		M / F	1 2	3 4	/		Y / N	Y / N
	6		M / F	1 2	3 4	/		Y / N	Y / N
	7		M / F	1 2	3 4	/		Y / N	Y / N
	8		M / F	1 2	3 4	/		Y / N	Y / N
	9		M / F	1 2	3 4	/		Y / N	Y / N
	10		M / F	1 2	3 4	/		Y / N	Y / N
	11		M / F	1 2	3 4	/		Y / N	Y / N
	12		M / F	1 2	3 4	/		Y / N	Y / N
	13		M / F	1 2	3 4	/		Y / N	Y / N
	14		M / F	1 2	3 4	/		Y / N	Y / N
	15		M / F	1 2	3 4	/		Y / N	Y / N

LIVING WOMEN OF CHILDBEARING AGE (15 – 49 years)

Person no. from table 1 above.	Literate ?	Night blind- ness	Goiter	Preg- nant now?	No. of doses tetanus vaccine	MUAC (cms)	Weight (kgs)	Height (cms)	Hemoglobin (gms)
	Y/N	Y / N	Y / N	Y / N				,,,	
	Y/N	Y / N	Y / N	Y / N				,,	, ,
	Y/N	Y / N	Y / N	Y / N		,	,	,,	, ,
	Y/N	Y / N	Y / N	Y / N		,,	,	,,	,,
	Y/N	Y / N	Y / N	Y / N		,,	,	,,	,,
	Y/N	Y / N	Y / N	Y / N		,	,	,,	,,
	Y/N	Y / N	Y / N	Y / N		,	,	,,	,,
	Y/N	Y / N	Y / N	Y / N		,	,	,,	,,
	Y/N	Y / N	Y / N	Y / N		,	,	,	,
	Y/N	Y / N	Y / N	Y / N					

Clus	ster number:	HH:	_ Child's person number:	Mot	ner's pers	son number:				
Que	stions for adult ca	retaker								
1) F	Relationship of res	pondent to ch	ild:	. Mother	Father	Grandmothe	er Grand	dfathe	r O	ther
2) I	s this child's mothe	er alive?					.Yes	/ N o	/	Unk
3) 5	Sex						M a	le /	Fer	nale
4) [Date of birth OR Ag	ge in months.			/	/	OR _		mo	nths
				[Day Mo	onth Year.				
5) [Does this child hav	e difficulty see	eing at night or in the evenin	g when ot	her peop	ole do not?	Yes	N o	/	Unk
6) 5	Since this time yes	terday, has th	is child breast fed?				Yes /	N o	/	Unk
	6a) If YES, was	breast milk th	is child's main source of foo	d since ye	sterday?		Yes ,	/ N o	/	U nk
	6b) If YES, how	long after birt	h did this child first breastfee	ed?			······		_ h	ours
7) \$	Since this time yes (circle all that are)	terday, has th true) P	is child received anything ot owered milk or infant formul	her than b a / S emi-	reast mil solid or s	lk? solid food / No	Water, one of t	tea, c hese	or ju	ice /
8) \$	Since this time yes	teday, has thi	s child drunk anything from a	a bottle wi	th a nipp	le?	.Yes	/ N o	/	Unk

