9) H	Has this child recei (show example)	ved any vitar	in A? Vitamin A is given as	drops fron	n a capsi	ule	Yes	N o	/	U nk
10)	Since 2 weeks ago	o, has this chi	d had diarrhea? Diarrhea is	3 or more	e stools i	n 24 hours	.Yes	/ N o	/	Unk
	10a) If YES, was	s this child tak	en to a clinic or hospital for	this proble	em?		.Yes	/ N o	/	Unk
11)	Since two weeks a	ago, has this c	hild had fever and difficulty	breathing	·		.Yes	/ N o	/	Unk
	10a) If YES, was	s this child tak	en to a clinic or hospital for	this proble	em?		.Yes	/ N o	/	Unk
12)	Since the change This vaccine is g	of governmen given by inject	t, has this child received me ion.	asles vac	cination?		.Yes	/ N o	/	U nk
Exa	mination of child									
13)	Bitot's spots							Yes	/	No
14)	Gums bleeding sp	ontaneously.						Yes	/	Νο
15)	Gums bleed upon	tapping						Yes	/	Νο
16)	Angular stomatitis						······	Yes	/	Νο
17)	Pallor in palms of I	hands						Yes	/	No
18)	BCG scar							Yes	/	No
19)	Row of ricketts							Yes	/	No
20)	Perifollicular hemo	orrhage						Yes	/	No
21)	Swollen joints – so	oft and painful						Yes	/	Νο
22)	Swollen joints – ha	ard and not pa	inful					Yes	/	Νο
23)	Bruises or eccymo	sis on legs						Yes	/	No
24)	Bowed legs							Yes	/	No
25)	Bilateral edema							Yes	/	No
26)	Spinal deformity							Yes	/	No
27)	Does this child hav	ve a physical	deformity making it difficult to	o obtain a	n accura	te height?		Yes	/	No
Anth	propometry and lat	poratory								
28)	Weight: (kgs)							,	·	
29)	Length/Height: (cn	ns)						,		
30)	MUAC: (cms)									
31)	Hemoglobin:

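### The protocol treats edema as acute malnutrition that voids weight-based indices, yet its child case definition uses z-scores alone and has no place for edema

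*Protocol*

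**What the plan says.** Four parts of the protocol bear on this.

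- **Objectives, item 1** names the target: "Estimate the current prevalence of acute malnutrition (wasting) and chronic malnutrition (stunting) among children 6-59 months of age". Acute malnutrition and wasting are treated as one quantity.
- **Case definitions, protein-energy malnutrition in children under 5** gives the rule: "Children with z-scores below -2 for weight-for-height, height-for-age, or weight-for-age are defined as wasted, stunted, or underweight, respectively". For the severe grade: "Z-scores less than -3 define severe wasting, severe stunting, or severe underweight". The alternative measure is a fallback: "mid-upper arm circumference (MUAC) is sometimes used to assess protein-energy malnutrition when measuring weight and height are not feasible". None of these mentions edema.
- **Variables, III.D.2** lists edema beside weight, height and MUAC as a component of acute protein-energy malnutrition.
- **Data collection, Physical examination** makes inspection for edema compulsory, in children and adults, whenever this type of malnutrition is assessed. The purpose is to "rule out edematous malnutrition which invalidates those anthropometric indices which include weight".

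The example child form in Appendix 1 has a yes/no item for "Bilateral edema". The only stated exclusion of indices, under Bias in data collection, measurement and analysis, concerns outlying values. Nowhere does the protocol say how a child with edema enters the numerator or the denominator.

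On use of the result, Intended and potential use of the findings says that the type of feeding program "is often largely determined by the prevalence of acute protein-energy malnutrition in children less than 5 years of age".

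**The concern.** The protocol calls edema a form of acute malnutrition, requires that it be looked for, and declares the weight index void when it is found. It then defines cases only by that index. A condition that is searched for and recorded cannot be counted under the written rule.

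The estimate affected is that of the first objective, in the group whose nutritional status the sampling section describes as often the primary interest. The severe category is most exposed: it is the smaller one, so a given number of uncounted children is a larger share of it. The section on anticipated products ties therapeutic feeding to severe protein-energy malnutrition. Stunting is not affected, because height-for-age does not use weight.

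**Working it through.** **1. The plan's own figure.** The sample size table gives 492 children for wasting at 20%, precision 5 points, design effect 2:

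n = DEFF × 1.96² × p(1−p) / d² = 2 × 3.8416 × 0.20 × 0.80 / 0.05² = 491.7, rounded up to 492.

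This reproduces and is not disputed. It supplies the 20% planning value and the 5-point yardstick.

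**2. Inputs.**
- w = 0.20, wasting among children without edema: the table's planning value, applied here to that group.
- s = 0.03, severe wasting among children without edema: an assumption.
- e = 0.5% to 4%, prevalence of bilateral edema: an assumption.
- f = share of children with edema whose weight-for-height z-score is still below −2: unknown, 0 to 1.

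**3. Formulas.**
- Prevalence with edema counted: w(1−e) + e. For the severe grade: s(1−e) + e.
- Route A, children with edema dropped: the estimate is w (or s). Shortfall = e(1−w), or e(1−s).
- Route B, children with edema kept and judged on z-score: the estimate is w(1−e) + f·e. Shortfall = e(1−f).

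Neither shortfall can be negative, so neither route overstates. Route B gives zero only if e = 0 or f = 1. Route A gives zero only if e = 0.

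**4. Results, Route A.**

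| Edema e | Acute, edema counted | Reported | Shortfall (points) | Severe, edema counted | Reported | Shortfall (points) |
|---|---|---|---|---|---|---|
| 0.5% | 20.4% | 20.0% | 0.4 | 3.5% | 3.0% | 0.5 |
| 1% | 20.8% | 20.0% | 0.8 | 4.0% | 3.0% | 1.0 |
| 2% | 21.6% | 20.0% | 1.6 | 4.9% | 3.0% | 1.9 |
| 4% | 23.2% | 20.0% | 3.2 | 6.9% | 3.0% | 3.9 |

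Example at e = 4%: 0.20 × 0.96 + 0.04 = 0.232, and 0.03 × 0.96 + 0.04 = 0.0688.

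**5. Results, Route B, acute malnutrition.** With f = 0 the shortfall equals e, so 0.5 to 4 points. With f = 0.5 it is half that, 0.25 to 2 points. With f = 1 it is nil.

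**6. Against sampling error.** The overall shortfall lies below 5 points at every assumed value. For the severe grade at 3%, with n = 492 and design effect 2, the 95% half-width is 1.96 × √(2 × 0.03 × 0.97 / 492) = 0.021, or 2.1 points. The severe shortfall is below this at 0.5%, 1% and 2% edema and above it at 4%. A larger sample narrows the interval but leaves the shortfall unchanged.

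**The case against.** **A reader might infer that the protocol drops these children or counts them as not wasted, so that its prevalence is shown to be too low.** The documents do not support that. No section states either handling, and the analysis section works through hemoglobin only. Judging the child on z-score would also go against the Physical examination text, and even then a child with edema whose z-score is below −2 is counted. What remains is narrower: the written rule allows only these outcomes, and none of them raises the estimate.

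**The handling may sit in an analysis plan not at hand.** A rule for missing or invalid indices could. But the case definitions are fixed in this protocol, and the analysis section refers back to that section for its thresholds. A stated definition that cannot count a stated form of the condition is more than a detail left for later.

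**The quoted sentence correctly defines wasting, an anthropometric category.** True, and z-score wasting is worth reporting as such. The difficulty arises because Objective 1 makes wasting stand for acute malnutrition while the variable list does not.

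**The size is assumed.** This stands. Neither the edema range nor the 3% severe base is in the documents. It is tempting to say that the severe figure could be more than doubled (6.88 / 3.00 = 2.29), but that takes the top of an assumed range over a small assumed base.

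**The prevalence does not alone settle programs.** Also fair: the protocol says it often largely determines them, and therapeutic feeding goes to individually identified persons.

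**Conclusion.** The inconsistency is real and internal to the protocol; no outside standard is needed to see it. Its direction is certain once edema counts as acute malnutrition, which is how the variable list treats it: the estimate is unchanged or too low, never too high. Its size is not established. Under the assumptions above it is modest for acute malnutrition overall and potentially material for the severe category, and it disappears in a population without edema. Because this is a generic protocol for many emergencies, the definition should hold where edema is common as well as where it is rare.

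A secondary inconsistency concerns adults. The edema examination is required for them too, but neither the women's variable list nor the Appendix 1 table headed "LIVING WOMEN OF CHILDBEARING AGE" has a field for it. A reader might infer that women will not be examined. The documents do not support that, because the list is of variables that may be collected and the form is offered as an example from one survey.

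**What to change.** Reconcile Objective 1, the child case definitions, the variable list and the Physical examination text through a survey classification that states:

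1. Acute malnutrition is weight-for-height z-score below −2, or bilateral edema, or both. Severe acute malnutrition is z-score below −3, or bilateral edema, or both.
2. Weight-based indices are not computed for children with bilateral edema. These children stay in the denominator and count as cases in both lines of item 1.
3. Wasting by z-score alone is reported as a separate line, with its denominator given as children without edema.

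This governs how survey results are classified, not how any child is managed.

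For adults, either add an edema field to the women's variable list and example form, or bring the examination requirement into line with what is recorded.

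The cost is a few sentences and at most one column; the example form already records bilateral edema for each child. If a survey is sized on the combined measure at the same precision and design effect, the formula above gives 507 children at 1% edema (p = 0.208) and 521 at 2% (p = 0.216), against 492.
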